1. OBJECTIVES

To evaluate whether ivabradine lowers resting heart rate and improves exercise duration in survivors of lymphoma with mediastinal involvement (including both Non-Hodgkin's Lymphoma and Hodgkin's Lymphoma) with evidence of radiation-induced autonomic dysfunction, manifested as a resting heart rate ≥ 80 bpm.

1.1 Study Design

This is a single center Phase II/pilot study to evaluate the safety and efficacy of ivabradine in survivors of lymphoma with mediastinal involvement (including both Non-Hodgkin's Lymphoma and Hodgkin's Lymphoma) with post-radiation cardiac autonomic dysfunction, manifested as a resting heart rate ≥ 80 bpm. This study is a randomized, double-blind, placebo-controlled, parallel design trial.

1.2 Primary Objectives

To evaluate whether ivabradine reduces resting heart rate compared to placebo in survivors of lymphoma with mediastinal involvement (including both Non-Hodgkin's Lymphoma and Hodgkin's Lymphoma) who were treated with mediastinal/mantle radiation and have a resting heart rate ≥ 80 bpm.

1.3 Secondary Objectives

To evaluate whether ivabradine improves exercise duration compared to placebo in survivors of lymphoma with mediastinal involvement (including both Non-Hodgkin's Lymphoma and Hodgkin's Lymphoma) who were treated with mediastinal/mantle radiation and have a resting heart rate ≥ 80 bpm.

1.4 Exploratory Objectives

- (i) To evaluate whether ivabradine improves additional markers of cardiac sympatho-vagal balance compared to placebo in survivors of lymphoma with mediastinal involvement (including both Non-Hodgkin's Lymphoma and Hodgkin's Lymphoma) who were treated with mediastinal/mantle radiation and have a resting heart rate ≥ 80 bpm.
- (ii) To evaluate whether ivabradine improves health related quality of life compared to placebo in survivors of lymphoma with mediastinal involvement (including both Non-Hodgkin's Lymphoma and Hodgkin's Lymphoma) who were treated with mediastinal/mantle radiation and have a resting heart rate ≥ 80 bpm.

2. BACKGROUND

2.1 Study Disease(s)

Thoracic radiation therapy (RT) is associated with an increased risk of cardiovascular morbidity and mortality.^{1,2} In particular significant delayed cardiotoxicity has been observed among long-term survivors of Hodgkin lymphoma (HL) treated with mantle/mediastinal radiation.^{3,4} These patients also frequently report exercise intolerance. Elevated resting heart rate and abnormal heart rate recovery following exercise are established markers of cardiac autonomic dysfunction⁵ and are strongly associated with cardiovascular morbidity and mortality in the general population

⁶⁻¹¹ as well as in survivors of Hodgkin lymphoma treated with mediastinal RT.¹²

Heart rate and rhythm are largely regulated by the autonomic nervous system. Parasympathetic influence is mediated via acetylcholine release by the vagus nerve and sympathetic influences are mediated via the secretion of epinephrine and norepinephrine. Acetylcholine reduces heart rate by increasing the potassium conductance of pacemaker cells in the sino-atrial node¹³ and inhibiting the hyperpolarization activated I_f channel to delay slow diastolic depolarization.¹⁴ Conversely, sympathetic activation increases intracellular calcium¹⁵ and activates the I_f channel¹⁶ to accelerate slow diastolic depolarization and increase heart rate. We have previously shown that thoracic RT is associated with autonomic dysfunction, as measured by elevated resting heart rate and abnormal heart rate recovery.¹² Furthermore, we were the first to report that these abnormalities are associated with impaired exercise tolerance among 263 Hodgkin lymphoma survivors treated with RT. Exercise duration was significantly reduced among RT patients with an elevated resting heart rate (9.2 ± 2.9 versus 10.7 ± 3.1 minutes, $p < 0.0001$) and those with abnormal heart rate recovery (8.3 ± 3.1 versus 10.6 ± 2.9 minutes, $p < 0.0001$).¹² We hypothesize that this is related to depressed parasympathetic stimulation secondary to RT-induced injury to the vagus nerve.

RT may also affect cardiovascular sympathetic function in Hodgkin lymphoma survivors. We have previously shown that thoracic RT is associated with a blunted systolic blood pressure (BP) response to exercise (OR 1.88, 95% CI 1.25-2.81).¹² In unpublished data, we compared supine and standing systolic BPs of 200 RT patients and 517 age, sex and cardiovascular risk-score matched control patients. The mean \pm SD postural decrease in SBP was significantly greater in the RT cohort compared to controls: -4.7 ± 9.9 versus -2.7 ± 10.8 mmHg, $p = 0.02$. The prevalence of orthostatic hypotension (defined as a postural decrease in SBP of ≥ 20 mmHg or a postural decrease in DBP of ≥ 10 mmHg) was 7.5% in the RT cohort. Such BP abnormalities predispose to intolerance of traditional atrioventricular node blocking drugs such as beta-blockers or calcium channel blockers that might be considered for this patient cohort with elevated resting heart rates who describe exercise intolerance.

2.2 IND Agent(s): N/A

The FDA has deemed this study exempt from an IND (see attached FDA correspondence).

2.3 Other Agents

Ivabradine is a hyperpolarization-activated cyclic nucleotide-gated channel blocker that reduces the spontaneous pacemaker activity of the cardiac sinus node by selectively inhibiting the I_f current, resulting in heart rate reduction with no effect on ventricular repolarization and myocardial contractility. Ivabradine causes a dose-dependent reduction in heart rate. The size of the effect is dependent on the baseline heart rate (i.e., greater reduction occurs in subjects with higher baseline heart rate). At recommended doses (2.5-7.5 mg twice daily), HR reduction is approximately 10 bpm at rest and during exercise. Analysis of HR reduction vs. dose indicates a plateau effect at doses > 20 mg twice daily. Ivabradine increases the uncorrected QT interval with HR slowing but does not cause rate-corrected prolongation of QT.

Following oral administration, peak levels of ivabradine are reached in approximately 1 hour under fasting conditions. The oral bioavailability is about 40% due to first pass metabolism in

the gut and liver. Food delays absorption by 1 hour and increases plasma exposure by 20-40%. Therefore, it is recommended that ivabradine be taken with food. It is about 70% plasma-protein bound with a volume of distribution of approximately 100 L at steady state.

Ivabradine is metabolized by the liver and intestines via CYP3A4 mediated oxidation. The major metabolite is the N-desmethylated derivative (S 18982), which is equipotent to ivabradine and circulates at concentrations approximately 40% that of ivabradine. The N-desmethylated derivative is also metabolized by CYP3A4. Ivabradine plasma levels decline with a distribution half-life of 2 hours and an effective half-life of approximately 6 hours. The total clearance of ivabradine is 24 L/h, and renal clearance is approximately 4.2 L/h, with ~ 4% of an oral dose excreted unchanged in urine. The excretion of metabolites occurs to a similar extent via feces and urine. No adjustment in dose is required for hepatic or renal dysfunction. Due to the fact that it is metabolized by CYP3A4, concomitant administration of others drugs that are metabolized by CYP3A4, such as ketoconazole, diltiazem, verapamil, grapefruit juice and St. John's wart is not recommended.

Ivabradine is well tolerated with a similar incidence of adverse effects when compared to placebo in a large (n=6,505) clinical trial involving patients with chronic systolic heart failure (SHIFT: Systolic Heart Failure Treatment with the I_f Inhibitor Ivabradine Trial).¹⁷ It is approved by the FDA to decrease heart failure related deaths and hospitalizations in patients with systolic heart failure (LVEF ≤ 35%) who have a resting HR ≥ 70 beats per minute despite maximal tolerated doses of beta-blockers. We wish to investigate whether ivabradine can achieve HR reduction in patients with a resting heart rate ≥ 80 bpm as a consequence of thoracic RT irrespective of baseline LVEF, and if so whether observed reductions in HR translate into improvements in exercise capacity. In addition, we wish to investigate whether ivabradine improves cardiac sympatho-vagal balance and patient-reported quality of life in this cohort. To date, this will be the first randomized trial of any therapeutic agent in the management of these patients. We will use a dose scheme similar to that used in the SHIFT trial.¹⁷

Matching placebo tablets will be manufactured and supplied by the Investigational Drug Pharmacy at Brigham and Women's Hospital.

2.4 Rationale

Survivors of mediastinal RT have increased cardiovascular morbidity and mortality. We have previously shown that thoracic RT is associated with cardiac autonomic dysfunction, as manifested by elevated resting HR and abnormal HRR after exercise.¹² Furthermore, we were the first to report that these abnormalities are associated with impaired exercise tolerance and increased mortality (for HRR only) among 263 HL survivors treated with RT.¹² Furthermore, HL survivors treated with RT had a blunted BP response to exercise.¹² Ivabradine is a drug that lowers HR without significantly impacting BP. We hypothesize that ivabradine will lower HR in HL survivors treated with RT. We further hypothesize that this reduction in HR will lead to increased exercise capacity, improved sympatho-vagal balance, and improved health related quality of life in these patients.

2.5 Correlative Studies Background: N/A

3. PARTICIPANT SELECTION

3.1 Eligibility Criteria

- 3.1.1 Survivors of mediastinal lymphoma (either Non-Hodgkin's Lymphoma or Hodgkin's Lymphoma) with no active malignancy
- 3.1.2 Prior mediastinal or mantle radiation ≥ 5 years prior to enrollment in the study
- 3.1.3 Age 18-80 years. Patients < 18 years will be excluded since ivabradine has not previously been studied in children. Patients > 80 years will be excluded since patients have to be able to perform a treadmill exercise stress test as part of this study.
- 3.1.4 ECOG performance status: N/A
- 3.1.5 Life expectancy: N/A
- 3.1.6 Participants must have normal organ function as defined below:
 - AST(SGOT)/ALT(SGPT) $\leq 2.5 \times$ institutional upper limit of normal
 - creatinine clearance ≥ 15 mL/min/1.73 m² for participants with creatinine levels above institutional normal.
- 3.1.7 Normal sinus rhythm with resting heart rate ≥ 80 bpm on screening EKG
- 3.1.8 Based on findings in animals, ivabradine may cause fetal harm when administered to a pregnant woman. For this reason, women of child-bearing potential must agree to use highly effective contraception (as described in Appendix A) prior to study entry and for at least 2 weeks after the last dose of ivabradine. Should a woman become pregnant or suspect she is pregnant while she or her partner is participating in this study, she should inform her treating physician immediately.
- 3.1.9 Ability to understand and the willingness to sign a written informed consent document.

3.2 Exclusion Criteria

- 3.2.1 Participants who are receiving any other investigational agents.
- 3.2.2 History of allergic reaction to *ivabradine*. Ivabradine is the first selective I_f channel sinus node inhibitor and therefore there are no other available drugs in this class.

- 3.2.3 Participants receiving any medications or substances that are inhibitors or inducers of cytochrome P450 3A4 are ineligible. Because the lists of these agents are constantly changing, it is important to regularly consult a frequently-updated list such as <http://medicine.iupui.edu/clinpharm/ddis/table.aspx>; medical reference texts such as the Physicians' Desk Reference may also provide this information. As part of the enrollment/informed consent procedures, the patient will be counseled on the risk of interactions with other agents, and what to do if new medications need to be prescribed or if the patient is considering a new over-the-counter medicine or herbal product.
- 3.2.4 Uncontrolled intercurrent illness including, but not limited to, ongoing or active infection, symptomatic congestive heart failure, acute coronary syndrome, symptomatic known coronary artery disease, severe valvular heart disease, active malignancy, or psychiatric illness/social situations that would limit compliance with study requirements.
- 3.2.5 Pregnant women are excluded from this study because ivabradine is an agent with the potential for teratogenic effects. Because there is an unknown but potential risk for adverse events in nursing infants secondary to treatment of the mother with ivabradine, breastfeeding should be discontinued if the mother is treated with ivabradine.
- 3.2.6 HIV-positive participants on combination antiretroviral therapy are ineligible because of the potential for pharmacokinetic interactions with ivabradine.
- 3.2.7 Patients with systolic blood pressure < 90 mm Hg.
- 3.2.8 Patients with sick-sinus syndrome, sino-atrial block, third degree heart block, atrial fibrillation, and those with permanent pacemakers.
- 3.2.9 Patients with other established indications for ivabradine: stable, symptomatic chronic HF with a left ventricular ejection fraction $\leq 35\%$ and in sinus rhythm with a resting HR ≥ 70 bpm, who are taking maximally tolerated doses of beta-blockers or have contraindications to beta-blocker use.
- 3.2.10 Patients with severe hepatic dysfunction (Child Pugh Class C)
- 3.2.11 Patients who have had chemotherapy or radiotherapy within 4 weeks (6 weeks for nitrosureas or mitomycin C) prior to entering the study or those who have not recovered from adverse events due to agents administered more than 4 weeks earlier will be excluded.

3.3 Inclusion of Women and Minorities

Both men and women of all races and ethnic groups are eligible for this trial.

4. REGISTRATION PROCEDURES

4.1 General Guidelines for DF/HCC Institutions

Institutions will register eligible participants in the Clinical Trials Management System (CTMS) OnCore. Registrations must occur prior to the initiation of protocol therapy. Any participant not registered to the protocol before protocol therapy begins will be considered ineligible and registration will be denied.

An investigator will confirm eligibility criteria and a member of the study team will complete the protocol-specific eligibility checklist.

Following registration, participants may begin protocol therapy. Issues that would cause treatment delays should be discussed with the Overall Principal Investigator (PI). If a participant does not receive protocol therapy following registration, the participant's registration on the study must be canceled. Registration cancellations must be made in OnCore as soon as possible.

Following randomization by ODQ to ivabradine or placebo, ODQ will send subject registration information to the unblinded investigational pharmacy staff at [contact].

4.2 Registration Process for DF/HCC Institutions

DF/HCC Standard Operating Procedure for Human Subject Research Titled *Subject Protocol Registration* (SOP #: REGIST-101) must be followed.

4.3 General Guidelines for Other Investigative Sites: N/A

4.4 Registration Process for Other Investigative Sites: N/A

5. TREATMENT PLAN

5.1 Treatment Regimen

A total of 60 eligible patients will be randomized to ivabradine or placebo. Ivabradine or placebo will be administered for a total of 6 weeks. Treatment will be administered on an outpatient basis. On assessment days, no dose holds will occur. Reported adverse events and potential risks are described in Section 7.

Ivabradine will be started at a dose of 5 mg p.o. twice daily with meals. The patient will then be assessed after 2 weeks and the dose will be adjusted as shown in the Table below:

Heart Rate	Dose Adjustment
> 60 bpm	Increase dose to 7.5 mg p.o. twice daily
50-60 bpm	Maintain dose at 5 mg p.o. twice daily
< 50 bpm or signs and symptoms of bradycardia	Decrease dose to 2.5 mg p.o. twice daily

If the patient continues to have symptomatic bradycardia or HR < 50 on 2.5 mg twice daily, ivabradine will be discontinued.

If symptomatic bradycardia occurs on ivabradine 7.5 mg or 5 mg twice a day at any point in the study, without objective hemodynamic compromise (SBP > 80 mm Hg), the medication can be resumed at a lower dose (2.5 mg reduction) after a 24 hour drug-free interval (i.e. 1 missed dose). If symptomatic bradycardia persists despite dose reduction, then the study drug will be further reduced by 2.5 mg or discontinued as per the discretion of the investigator. A maximum of 2 dose reductions would be allowed for patients on 7.5 mg twice daily and 1 dose reduction for those on 5 mg twice daily. Patients requiring dose reduction will not have a subsequent dose escalation at any point during the study.

Placebo will be used in a similar manner. Patients will be maintained on the best tolerated dose for a total of 4 weeks.

Patients randomized to either ivabradine or placebo will be asked to maintain a drug diary as detailed in Appendix B to assess compliance.

5.2 Pre-Treatment Criteria

5.2.1 Screening Visit: After written informed consent is obtained, we will:

- a) Obtain a detailed history and physical examination
- b) Obtain an EKG to make sure that patients meet eligibility criteria i.e. are in sinus rhythm, have a resting HR \geq 80 bpm, and do not have evidence of high grade AV block.
- c) Review laboratory values obtained within the last 12 months for liver and renal function as described in the inclusion/exclusion criteria.

5.2.2 Baseline Visit: In addition to a detailed history and physical examination, we will:

- a) Obtain an EKG to make sure that patients are in sinus rhythm, have a resting HR \geq 80 bpm, and do not have evidence of high grade AV block prior to study drug randomization.
- b) Obtain a urine pregnancy test to ensure that women of child-bearing age are not pregnant prior to study drug randomization.

5.2.3 2 week visit: In addition to a detailed history to review side effects from study drug treatment, we will:

- a) Obtain an EKG to assess heart rate to determine dose adjustment as stated in section 5.1.

5.2.4 6 week visit: In addition to study procedures outlined below, we will:

- a) Obtain a pregnancy test to ensure that women of child bearing age are not pregnant.

5.3 Agent Administration

Patients will take ivabradine or placebo for a total of 6 weeks. Ivabradine will be started at a dose of 5 mg p.o. twice daily with food. Ivabradine or placebo must not be crushed, chewed, or dissolved in water. The dose will be adjusted as per the Table in section 5.1 at the 2 week visit. Patients will continue the maximal tolerated dose for an additional 4 weeks. Placebo will be administered in a similar manner.

Ivabradine is FDA approved to reduce heart failure hospitalizations in patients with systolic heart failure (left ventricular ejection fraction $\leq 35\%$) who have resting HR > 70 bpm, despite maximal tolerated doses of beta-blockers. This study is evaluating ivabradine for a non-FDA approved indication and the drug titration protocol is per the Table in section 5.1.

Ivabradine is metabolized by the liver and intestines via CYP3A4 mediated oxidation. Therefore, patients will be instructed to avoid other drugs metabolized by the CYP3A4 system and grapefruit, star fruit, and pomegranate, in any form, for the duration of the study.

Patients will be asked to maintain a drug diary to assess compliance during the study. Patients will be instructed to note a missed or vomited dose and take the next dose as scheduled.

5.3.1 CTEP and/or CIP IND Agent(s), or other IND agent: N/A

5.3.2 Other Agent(s): N/A

5.3.3 Other Modality(ies) or Procedures

All patients will have a standard 12 lead EKG performed at the screening, baseline, 2 week and 6 week visits.

All patients will undergo exercise treadmill testing at the baseline and 6 week visits.

All patients will have a 24 hour ambulatory Holter monitor placed at the baseline and 6 week visits.

All patients will complete the SF-36 quality of life questionnaire at the baseline and 6 week visits.

Due to cost constraints, a subset of patients (n=30) will undergo further sophisticated autonomic function testing at the baseline and 6 week visits. Depending on scheduling limitations, they may have to return for a second day at each of these visits to complete the additional autonomic function tests.

a) Exercise treadmill testing

All exercise stress tests will be performed in the cardiovascular stress testing laboratory at Brigham and Women's Hospital by trained exercise physiologists under the supervision of a staff

cardiologist. Patients will avoid consumption of all caffeine containing products for 24 hours prior to exercise treadmill testing. All patients will undergo exercise treadmill testing using a symptom-limited Bruce protocol according to established guidelines.¹⁸ Exercise will be continued until one or more of the following endpoints: exhaustion, symptom limitation, $\geq 85\%$ of age-predicted maximal HR, ≥ 10 mmHg drop in systolic blood pressure (SBP) from baseline, sustained ventricular tachycardia, ST-segment depression ≥ 3 mm measured 80 msec after the J junction, or ST-segment elevation of ≥ 1 mm.

b) 24 Hour Ambulatory Holter Monitor

All patients will have a 24 hour ambulatory Holter monitor placed at baseline prior to study drug initiation and at the 6 week time point, prior to study drug termination. Holter monitors will be placed by the cardiology department at Brigham and Women's Hospital. Patients will be asked to return the Holter monitor in person or via mail to Brigham and Women's Hospital.

c) SF-36 Quality of Life Questionnaire

All patients will be asked to complete short form 36 (SF-36) quality of life healthcare questionnaires at the baseline and 6 week visits.

d) Sophisticated autonomic function testing

All of the additional autonomic function tests will be performed by [name] in the autonomic function testing laboratory at Faulkner Hospital. Cardiac autonomic function will be assessed using:

1. Deep breathing:

Deep breathing tests cardiac parasympathetic functions. All subjects will be asked to avoid smoking, intake of caffeinated beverages, and strenuous exercise for 12 hours prior to the test. Subjects will be asked to empty their bladder before the test to prevent sympathetic over-activity. They will then be asked to lie quietly in a temperature-controlled room for 20 minutes. A baseline EKG recording will be obtained for one minute to ensure a stable resting heart rate. Subjects will then be asked to inhale and exhale slowly at a rate of 6 breaths/minute and a continuous EKG will be recorded during deep breathing. Respiratory sinus arrhythmia (RSA) amplitude, defined as the difference in heart rate between end expiration and end inspiration, will be recorded for each respiratory cycle and the average RSA will be reported.¹⁹

2. Valsalva maneuver:

Valsalva maneuver evaluates sympathetic adrenergic function using the blood pressure responses and parasympathetic function using the heart rate responses. The Valsalva maneuver consists of forced expiration against resistance with an expiratory pressure during strain of 40 mm Hg for 15 seconds. The maneuver will be performed in the supine position. Patients will be asked to breath into a 10 ml plastic syringe that is connected to a

pressure gauge. They will be asked to take a deep breath and blow into the syringe and keep the pressure at 40 mm Hg for 15 seconds. Subjects will be asked to practice the maneuver to ensure that they can do it correctly prior to the actual measurements. Once they have mastered the maneuver, they will be asked to rest for 3-5 minutes before repeating the maneuver. Heart rate and blood pressure will be recorded non-invasively using the Finapres NOVA system (Finapres Medical Systems, Netherlands). The Valsalva ratio, defined as the maximum heart rate during the maneuver divided by the lowest heart rate obtained within 30 seconds of the peak heart rate, will be measured.¹⁹

3. Tilt Testing:

Tilt tests predominantly evaluate adrenergic function by applying orthostatic stress. Patients will be placed in the supine position and baseline heart rate and blood pressure will be acquired over 5-10 minutes. The patient will then be tilted up to an angle of 70 degrees over 5-10 seconds. Patients will be closely observed for chest pain, shortness of breath, dizziness, lightheadedness or syncope. If they have no adverse reaction, the heart rate and blood pressure will be assessed every minute for 10 minutes. The patient will then be placed back in the supine position. The increase in heart rate and drop in blood pressure in response to the tilt will be recorded.¹⁹

4. Heart rate variability:

Heart rate variability with low frequency and high frequency oscillations in RR intervals assesses the balance of sympathetic and parasympathetic influences in the heart. Measures of overall heart rate variability and spectral analysis of heart rate variability will be performed with a Matlab based computer system.²⁰

5. Sudomotor testing

Electrochemical skin conductance (ESC) is a new noninvasive test for measurement of sudomotor functions.²¹ ESC correlates with loss of small fiber skin nerves, and it is useful for evaluation of small fiber neuropathy. Measurements using ESC will be performed as described previously.²²

The RSA and Valsalva ratio will be compared to age and gender based normative values (Tables 1 and 2). The cardiovagal composite autonomic severity score (CASS) will be calculated (Table 3). The adrenergic CASS will be calculated (Table 4).¹⁹

Table 1: Normal Values for Deep Breathing Test

Age range (years)	Minimum Normal RSA (beats/min)
10-29	≥ 14
30-39	≥ 12
40-49	≥ 10
50-59	≥ 9
60-69	≥ 7

Table 2: Normal Values for Valsalva Ratio

Age range (years)	Minimum Normal Valsalva Ratio	
	Women	Men
10-29	1.46	1.59
30-39	1.5	1.52
40-49	1.51	1.44
50-59	1.47	1.36
60-69	1.39	1.29

Table 3: Calculation of Cardiovagal Score

Result	Degree of Abnormality	Cardiovagal Score	Definition
Normal		0	
Abnormal	Mild	1	RSA or Valsalva ratio reduced but $\geq 50\%$ of minimal normal values
	Moderate	2	RSA or Valsalva ratio $< 50\%$ of minimal normal values
	Severe	3	Both RSA and Valsalva ratio $< 50\%$ minimal normal values

Table 4: Calculation of Adrenergic Score:

Result	Degree of Abnormality	Adrenergic Score	Definition
Normal	0		
Abnormal	Mild	1	Valsalva maneuver: Early phase 2 drop in BP: 20-40 mmHg OR Late phase 2 BP does not return to baseline OR Pulse pressure reduction $\leq 50\%$ of baseline OR Systolic pressure recovery time 4-5 seconds
	Moderate	2	Valsalva maneuver: Early phase 2 drop in BP: 20-40 mmHg AND Absent late phase 2 OR Absent phase 4 OR Systolic pressure recovery time 6-9 seconds
	Severe	3	Tilt: SBP reduction ≥ 30 mmHg; MAP reduction ≥ 20 mmHg OR Valsalva maneuver:

			Early phase 2 drop in BP \geq 40 mmHg AND Absent phase 2 AND Absent phase 4 OR Absent phases 2 and 4 systolic pressure recovery time = 10 seconds
	Severe	4	Tilt AND Valsalva maneuver responses in #3

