8.2 IND Agent #2: N/A

8.3 Other Agent #1: N/A

8.4 Other Agent #2: N/A

9. BIOMARKER, CORRELATIVE, AND SPECIAL STUDIES

9.1 Biomarker Studies: N/A

9.2 For IDE Protocols Only: Investigational Device Information: N/A

9.3 Laboratory Correlative Studies: N/A

9.4 Other Agent #2: N/A

10. STUDY CALENDAR

Baseline evaluations/tests are to be conducted within 1 week prior to start of protocol therapy. In the event that the participant's condition is deteriorating, laboratory evaluations should be repeated within 48 hours prior to initiation of therapy.

2 week study evaluations and drug up-titration should be administered within ± 3 days of the protocol-specified date, unless otherwise noted.

Week 6 study evaluations/tests should be conducted within ± 7 days of the protocol-specified date and should be completed prior to termination of study drug.

	Screening visit	Baseline	Week 2	Week 6
Agents:		Ivabradine vs. placebo	Ivabradine or placebo dose titration	Study End
Informed consent	X			
Demographics	X			
Medical history	X		X	X
Physical exam		X	X	X
Concurrent Meds	X	X	X	X
Vital signs	X	X	X	X
Height		X		X
Weight		X		X
Serum chemistry ^a	X			
EKG (as indicated)	X	X	X	X
B-HCG		X ^b		X ^b
Exercise stress test		X		X
24-hr ambulatory Holter monitor		X		X
SF-36 QOL questionnaire		X		X
Sophisticated autonomic function testing ^c		X		X
Adverse event evaluation		X-----X		
a: Review of SGOT [AST], SGPT [ALT], creatinine obtained within the last 12 months. b: Urine pregnancy test (women of childbearing potential). c: For subset of patients randomized to receive autonomic function testing				

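### The treadmill test also stops at 85% of age-predicted maximal heart rate, so ivabradine can lengthen exercise time in HR-stopped patients without any gain in capacity, and the analysis ignores why tests stopped

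*Combined protocol and SAP*

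**What the plan says.** **The test.** Section 5.3.3 a) states: "All patients will undergo exercise treadmill testing using a symptom-limited Bruce protocol according to established guidelines". The stopping rule follows: "Exercise will be continued until one or more of the following endpoints: exhaustion, symptom limitation". The same list then adds at least 85% "of age-predicted maximal HR", a fall in systolic pressure, sustained ventricular tachycardia, and ST-segment changes. Any one of these ends the test.

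**The drug.** Section 2.3 says that at recommended doses "HR reduction is approximately 10 bpm at rest and during exercise".

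**Timing.** Section 5.1: "On assessment days, no dose holds will occur". Section 10 says that week-6 evaluations "should be completed prior to termination of study drug". The second treadmill test is therefore done on treatment.

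**The endpoint.** Change in treadmill duration from baseline to week 6 is the only secondary endpoint (section 11.3). Section 13.6 compares it between arms by ANCOVA or the Quade test, adjusting for the two stratification factors. The reason for stopping plays no part. Section 2.3 says that the aim is to learn whether a lower heart rate translates into better exercise capacity, and section 13 states the hypothesis in the same terms.

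**The concern.** One of the criteria that ends the measurement is the quantity that the drug lowers. A patient who stops at the heart-rate limit at baseline and is then given ivabradine starts lower, reaches the same limit later, and is timed for longer, until symptoms or exhaustion intervene. A placebo patient gets no such shift. The difference favours ivabradine and needs no change in capacity. Randomisation and blinding do not remove it, because treatment itself causes it.

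At stake is how the only secondary endpoint is read. Duration would still be measured as the plan defines it. What is exposed is the step from longer duration to better exercise capacity. Without the stopping reasons, the trial's report could not show whether the artefact was trivial or a large part of the result.

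**Working it through.** **1. The plan's own figure.** Section 13.1 gives 27 per arm, 34% against 12% improvement, SD 24% and a type I error of 0.05. The net effect is 34 − 12 = 22 points. The standard error is 24 × √(2/27) = 6.53, so the noncentrality is 22/6.53 = 3.37. Two-sided t-test power is 91.1%, against 90% stated. The inputs are therefore read as the plan meant them.

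**2. Delay in reaching the limit.**
- From the documents: the 85% limit (section 5.3.3 a) and a 10 bpm reduction during exercise (section 2.3).
- Assumed: maximal HR of 220 minus age, HR rising linearly with time, resting HR 80-90 (eligibility requires at least 80), and the full 10 bpm reduction throughout the test.

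The limit is 0.85 × (220 − age). With a linear rise, delay ÷ own duration = 10 ÷ (limit − resting HR).

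| Age, resting HR | Limit | Limit − rest | Delay, % of own duration |
|---|---|---|---|
| 35, 80 | 157.25 | 77.25 | 12.9 |
| 50, 85 | 144.5 | 59.5 | 16.8 |
| 65, 90 | 131.75 | 41.75 | 24.0 |

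This assumes full reserve, meaning that the patient could have continued for the whole delay. For a test of 9.2 minutes (the mean in section 2.1 for irradiated survivors with elevated resting HR), the delay is 1.2 to 2.2 minutes. If exercise HR fell by only 5 bpm, the percentages would halve.

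**3. Effect on the comparison, with no true gain.** The shift in the arm mean is the share of tests stopped on HR × the delay. If half stop on HR, it is 6.5, 8.4 and 12.0 points for the three profiles.

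- Half stopped on HR, SD held at 24%: the chance of p<0.05 is 16%, 24% and 44%. Holding the SD fixed is slightly too generous, because a delay in only half of the ivabradine arm widens that arm's spread. Simulating the mixture gives about 16%, 23% and 40%, and these are the figures used here.
- A quarter stopped on HR, SD held at 24%: 8%, 10% and 15%.

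**4. Little reserve.** Suppose that an HR-stopped patient could have gone on for only 0-1 minute (uniform), with the limit at 9.2 minutes. The mean gain is 0.5/9.2 = 5.4%. With half of tests stopped on HR the shift is 2.7 points and the chance of p<0.05 is about 7%. With a quarter it is about 5%, essentially nominal.

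**5. Why restricting the analysis helps only partly.** A patient who stopped on symptoms at baseline can improve and then be cut off by the HR limit at week 6, and this happens sooner on placebo than on ivabradine. Section 13.1 itself allows a 12% improvement on placebo. The remaining bias has the same direction. Its size depends on how far such patients sit from the limit, which the documents do not say, so no figure is given.

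**The case against.** The strongest reply is that few tests may stop on heart rate. Section 2.1 says these survivors often report exercise intolerance, and section 13.3 stratifies on beta-blocker use, so beta-blocked patients are expected. Both point towards symptoms or exhaustion ending many tests. This stands. It is why the size is left open and why the low end of the illustration is close to the nominal 5%. It does not dispose of the point, because the planned analysis would not show whether it was so.

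A second reply is that duration is the stated endpoint and is measured as planned, in one secondary endpoint of a single-centre pilot study. That also stands. It confines the point to the capacity interpretation.

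A third is that the heart-rate limit may be a deliberate safeguard. Chest-irradiated patients are at raised cardiovascular risk, and section 3.2.4 excludes "symptomatic known coronary artery disease" but not silent disease. The documents do not give the reason for the limit. The objection is good enough that removing the limit should not be the lead recommendation.

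A reader might also infer that stopping reasons are not collected. The case report forms are not among the documents, so that cannot be said. What can be said is that section 13.6 does not use them.

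**Conclusion.** The point holds as a caution on interpretation that is cheap to act on. For any test that would stop on heart rate, the rule as written lengthens ivabradine durations independently of capacity, and the analysis cannot separate the two. The mechanism and its direction follow from the plan's own text.

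The size does not. The 13-24% delay, and the 16-40% or 7% chances of a significant result when half of tests stop on HR, rest on the assumed maximal-HR formula, linear rise, resting rates, share and reserve. They also take all patients in a scenario to have one age and resting HR, whereas eligibility is "Age 18-80 years". They show that the effect could range from negligible to a substantial part of the planned 22 points. They do not estimate it.

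A reader might go further and conclude that a positive duration result would be an artefact, or that the secondary endpoint is invalid. The documents do not support that: it would need most tests to stop on heart rate with ample reserve, and nothing in the plan says so. The primary endpoint, resting HR from the EKG, is untouched.

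**What to change.** 1. In section 5.3.3 a), require the reason for stopping to be recorded at both treadmill tests, and tabulate it by arm and visit.
2. In section 13.6, add a sensitivity analysis restricted to patients whose baseline test did not stop on heart rate. State that it reduces but does not remove the bias and that it has fewer patients.
3. State that improved exercise capacity will not be claimed from the unrestricted comparison alone.
4. Optionally, if the supervising cardiologist agrees that it is safe, remove the 85% heart-rate stop at both visits and keep the blood-pressure, ventricular tachycardia and ST stops. The test would then match its label.

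Steps 1 to 3 cost one recorded item per test, one table and one extra analysis, with no added patients, visits or patient risk. Stopping reasons may not be recoverable later, so step 1 should be in place before testing. Step 4 is a small edit to the text but takes some patients to higher exertion, and so is a clinical decision.
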